Perceived Self-Efficacy	CRF and Walking Self-management	PSE for Fatigue Self-Management (6 items), Walking Duration (12 items)	Pre & Post-Surgery Weeks 1-12	PSE for CRF self-management (.92) and PSE for walking duration (.95).
Perceived Self-Efficacy	Balance	Activities-specific Balance Confidence (16 items)	Pre & Post-Surgery Weeks 3, 6, 9, 12	PSE for balance for increasingly challenging activities (.82-.90).
CRF Self-Management Behaviors	Walking Exercise	Recorded in Daily Diary and electronically in the Wii Fit Plus	Weeks 1-12	Total number of minutes walked with the Wii per week.
CRF Self-Management Behaviors	Balance Exercise	Recorded in Daily Diary and electronically in the Wii Fit Plus	Weeks 1-12	Total number of balance exercises completed with the Wii per week.
Functional Status	Capacity	Fatigability; Six-minute Walk Test	Pre-Surgery, Prior to Chemo/Week 6, & 12	Degree of fatigue associated with walking during the six-minute walk test. Distance walked in six minutes.
Functional Status	Performance	SF-36 v2 – 8 subscales accounting for two components, physical and mental health (36 items)	Pre & Post-Surgery Weeks 3, 6, 9, 12	Performance of daily mental and physical activities that people do in the normal course of their lives (.78-.92)
Functional Status	Performance	Pedometer Daily Diary	Weeks 1-12	Performance in average number of steps taken per day per week
Quality of Life	Quality of Life	QOL Index: Overall QOL, Family, Health/Function, Socioeconomic, Psych/Spiritual (66 items)	Pre & Post Surgery Weeks 3, 6, 9, 12	Satisfaction with various aspects of life and the importance of each aspect of life to the person (.73-.99)

Legend: Surgery = Sx; CRF = Cancer-Related Fatigue. PSE = Perceived Self-Efficacy. Medical Outcomes Short Form-36 v2 = SF-36 v2. QOL = Quality of Life

Revision 5/19/2019. Updated Table with the following 3 measures added.

Table 3. Main Concepts, Variable, Measures, Collection Schedule, and Measurement Objective

Concept	Variable	Measure # Items	Schedule	Measurement Description (Cronbach's alpha)
Symptoms	Sleep Impairment	PROMIS v 1.0 Sleep-Related Impairment Short-Form 8a (8 Items)	Pre & Post-Surgery Weeks 3, 6, 9, 12	Degree of sleep-related impairment. (0.90)
Symptoms	Pain Source, Pain Treatment, Severity and Interference Information	The Brief Pain Inventory (4 Severity Items; 7 Interference items; 4 Source Items)	Pre & Post-Surgery Weeks 3, 6, 9, 12	Degree of pain severity and impact of pain on every day. living. (0.77 to 0.91)
Perceived Self-Efficacy	Pain Self-Management	The Perceived Self-Efficacy for Pain Self-Management Inventory (6 Items)	Pre & Post-Surgery Weeks 3, 6, 9, 12	Degree of pain self-management. (0.90)

Aim 2 – Measures – WCG Delayed Intervention. At the start of wk 7, WCG will begin the intervention, concluding at wk 12. Aim 1 study variables and measures (Table 3) will be analyzed for Aim 2 for wks 7-12 to compare with the IIG wks 1-6 outcomes.

Aim 3 – Measures – IIG Intervention Sustainability. At the start of wk 7, IIG participants will be given the option to extend the intervention an additional 6 wks. We will measure the extension rate as % participants who elect to extend. Adherence to the intervention will be measured as % participating in the intervention who adhered to prescribed intervention. Weekly adherence will be calculated by taking number of times prescribed intervention was completed divided by total number of interventions prescribed for week. These data are recorded in the Daily Diary and will be confirmed by research staff reviewing recorded data in Wii Fit-Plus. Retention, measured as part of sustainment, will be calculated as % who elected to extend 6 wks who completed final data collection at wk 12. Based on our conceptual definition of sustainability, we will measure the extent to which components of the intervention were rated acceptable for continued use by participant. Acceptability will be measured at end of wk 6 and 12 using a 15-item Acceptability Questionnaire (Appendix B1) using a numeric scale (1 to 6: 6 = agrees strongly) with higher scores indicating greater acceptability of the exercise program. The Questionnaire has a Flesch-Kinkaid 6th grade reading level and was successfully used in our R21 RCT and allows participants to rate how well barriers and facilitators to exercise are addressed. Open-ended questions provide further input.^{23,24} Efficacy will be measured using the same study variables and measures analyzed in Aim 1 (Table 3) for wks 7-12.

Section 8.0 Drug Formulation and Procurement

Not applicable. This study is not a pharmaceutical trial.

Section 9.0 Toxicity and Adverse Event Reporting Guidelines

Study Monitoring

The Principal Investigator of the study will monitor for all potential unanticipated problems that may involve risk to participants and will report adverse events (unanticipated problems), including serious adverse events in accordance to institutional policy. Continuous, close monitoring will occur in several ways. First, adverse events identified during implementation of the intervention are monitored through the nurse who assesses the participant on a weekly basis either by home and/or phone visit utilizing the Daily Diary. The nurse documents any adverse event reported by the participant and immediately reports the occurrence to the Principal Investigator. In addition, the Principal Investigator will monitor participants' Daily Diaries for adverse events and specifically, as it relates to Section 9.0 of this application, any and all adverse events will be reviewed, evaluated, and documented. Using a consultative approach, [name], the Principal Investigator, will ensure reporting of results from the data and safety review to the transdisciplinary team of Co-Investigators and Key Consultants occurring two times a year and more frequently when deemed necessary for the health and safety of participants.

Note: All 72 two-arm R21 RCT participants used the Daily Diary to record their daily study-related physical activity including number of steps recorded (pedometer).^{23,137-140} used successfully in the R21 RCT without participant complaint about burden. **Note:** In the R21 RCT, no adverse events were reported; participants had a mean age of 67 with a mean of 8 comorbid conditions. The Daily Diary is structured with an area for participants to report experiences related to problems or symptoms during or after exercising. This format of reporting adverse events is supported in the literature and discussed in the Study Protocol in the Research Design Section (Section 5.0) and Study Parameters Section (Section 7.0).¹³⁹ The nurse will review the Daily Diary once a week with the participant and more if necessary to evaluate for potential adverse events. Providing the participant with a means to record problems/symptoms (possible adverse events) will help the participant to develop skills to recognize CRF and other symptoms and effectively develop skills to interpret changes in symptoms and physical functioning.⁶⁷ Likewise, as the participant records the solution to the problems or symptoms (possible adverse events), the participant is building a personal database of health problems and solutions to draw from in the future which enhances their PSE for CRF self-management.⁶⁷ DeNijs and colleagues¹³⁸ reported in a systematic review of the general cancer population that persons with CRF did not adhere to an exercise regimen since they no longer felt certain about their bodies and needed support in order to self-manage fatigue. Thus, the nurse can enhance PSE to self-manage CRF through means of monitoring and interpreting symptoms using the diary to problem solve to make decisions regarding the effect of exercise on CRF and other outcomes. In addition, the Daily Diary outlines the safety procedures for the participant to follow before each exercise session. Moreover, the participant will have phone access seven days a week to contact the nurse should the participant identify or need support in managing problems or symptoms during or after exercising.

Auditing

Auditing is a systematic and independent examination of trial-related activities and documents to determine:

- whether the evaluated trial-related activities were conducted
- the data were recorded, analyzed, and accurately reported, according to the protocol, to the sponsor's SOPs, GCP, and applicable regulatory requirement(s).

Auditing is a Quality Assurance, one point snapshot of one subject.

This study will undergo audit on at least a quarterly basis by the UNMC Fred & Pamela Buffett Cancer Center Audit Committee.

Detailed policy and procedures for this section may be reviewed at:

<https://www.unmc.edu/cancercenter/clinical/prms.html>

FRED & PAMELA BUFFETT CANCER CENTER DATA AND SAFETY MONITORING COMMITTEE (DSMC) REPORTING

In its initial review, the DSMC will make a recommendation for the frequency of DSMC monitoring based on an assessment of risk associated with study-associated therapy, per the DSMC policy.

All adverse events grade three or higher (expected or unexpected, regardless of attribution) will be reported to the University of Nebraska Medical Center, Fred & Pamela Buffett Cancer Center DSMC in accordance with DSMC guidelines.

An adverse event (AE) is defined as any untoward medical occurrence in a subject or clinical investigation subject participating in a clinical trial, which does not necessarily have a causal relationship with protocol specified therapy. An adverse event can therefore be any unfavorable and unintended sign (including an abnormal laboratory finding), symptom, or disease temporally associated with the use of any investigational therapy/device or intervention, whether or not the event is considered causally related to the use of the product.

Any worsening of a pre-existing condition or illness is considered an adverse event. Laboratory abnormalities and changes in vital signs are considered to be adverse events if they result in discontinuation from the study, necessitate therapeutic medical intervention, meet protocol specific criteria and/or if the investigator considers them to be adverse events. In general, if a laboratory abnormality or change in vital sign is associated with a specific diagnosis that is being reported concurrently as an adverse event the findings that support the diagnosis do not need to be reported as separate adverse events unless the investigator feels it is appropriate.

Treatment-emergent Adverse Event: Treatment-emergent adverse event is defined as any adverse event with onset or worsening from the time of trial intervention until 30 days after the final protocol specified intervention.

Serious Adverse Event: A serious adverse event is one that at any dose (including overdose) and regardless of causality that:

- Results in death
- Is life-threatening 1
- Requires inpatient hospitalization or prolongation of existing hospitalization
- Results in persistent or significant disability or incapacity 2
- Is a congenital anomaly or birth defect
- Is an important medical event 3

1. “Life-threatening” means that the subject was at immediate risk of death at the time of the serious adverse event; it does not refer to a serious adverse event that hypothetically might have caused death if it were more severe. 2. “Persistent or significant disability or incapacity” means that there is a substantial disruption of a person’s ability to carry out normal life functions. 3. Medical and scientific judgment should be exercised in deciding whether expedited reporting is appropriate in situations where none of the outcomes listed above occurred.

Important medical events that may not be immediately life-threatening or result in death or hospitalization but may jeopardize the patient or may require intervention to prevent one of the other outcomes listed in the definition above should also usually be considered serious.

Attribution of AE/SAE: The investigator will determine the likelihood of relationship of the AE to the study based on the following definitions:

Not related: The subject was not exposed to the study treatment or another cause is obvious.

Probably not related: The AE is most likely explained by another cause, and the time of occurrence of the AE is not reasonably related to the study.

Possibly related: Study treatment administration and AE occurrence reasonably related in time, and the AE is explained equally well by causes other than study treatment, or treatment administration and AE occurrence are not reasonably related in time, but the AE is not obviously a result of other causes.

Probably related: Study treatment administration and AE occurrence are reasonably related in time, and the AE is more likely explained by study treatment than by other mechanisms.

Definitely related: The occurrence and timing of the AE are clearly attributable to the study treatment.

AEs will be collected from the time the subject signs the consent form until 30 days after the final protocol specified intervention. All AEs will be followed until resolution or a cause is identified. AEs judged by the investigator as not related or probably not related to the treatment will NOT be followed beyond the end of the study.

Section 10.0 Statistical Considerations

Statistical Analysis. All tests of hypotheses will be two-tailed at $\alpha=0.05$. We compare groups at baseline using parametric and non-parametric tests to assess equivalence of confounding physiological and contextual patient characteristics, and pre-surgical outcome variables. If substantive differences exist, they will be controlled for in subsequent analyses by regression techniques, guided by the degree of dissimilarity rather than strict statistical significance.¹⁴⁴

Primary analysis (Aim 1) is the comparison among study groups of the primary outcome CRF severity and fatigability assessed at approximately 6 wks post-surgery. Analysis is based on a regression model for both CRF scores with the following variables in the regression equation: baseline CRF, study group, age, and (if appropriate) plausible interaction between these variables. We test association of study group with outcomes.

In Aim 2 our hypothesis comparing outcomes in IIG and WCG by age group will be addressed in the context of a longitudinal analysis. There are 6 time-ordered differences between IIG and WCG. We use generalized linear (mixed) models to allow flexible correlation structures in the repeated measures.^{145,146} Our regression equation has in addition to the aforementioned variables: time (week) of assessment, and critically, study group with time interactions. The model allows us to test if group effects are changing over time – referred to as a “parallel” profile analysis.¹⁴⁷ If the hypothesis is supported, we test whether that average profiles (over time) in

the two groups are the same. Aim 3 concerns three binary responses in the IIG group at 6 wks: extension, retention, and adherence. Logistic regression models will be used to assess the influence of explanatory variables on the likelihood of outcome.¹⁴⁷⁻¹⁴⁹

Secondary Outcomes: An analogous strategy is applicable to continuous outcomes assessed at 12 wks. We will use linear models with the caveat that models are conditional on electing to extend participation. Statistical analysis will include intent-to-treat (ITT) analysis and per protocol analysis.^{150,151} ITT principle calls for making inference on the whole sample, with patients as randomized to their study group.¹⁵² To address missingness in our response data we will explore strategies for imputation.¹⁵³ The techniques described above allow missing at random (MAR). Inverse-probability weighting¹⁵⁴ will be investigated to accommodate missing data patterns that are not MAR. Assurance of analysis robustness and minimization of bias: We use a range of outcome measures based on the patient-centered principle to ensure the relevance of the study both biologically and practically. To enhance reproducibility, we will ensure protocol fidelity and follow our analytic plans, including addressing missing data in outcomes. To minimize analysis bias, we will adjust for factors such as potential between group unbalance and examine the robustness of our conclusions under deviations of model assumptions.

Note: Determination of Sample Size is discussed under the Research Design (Section 5, specifically, Section 5B)

TIMELINE. The research timeline is shown in Table 4.

POTENTIAL PROBLEMS AND ALTERNATIVE STRATEGIES. We acknowledge that NSCLC patients after surgery may be subject to complications requiring a break from the intervention. Should participants report unmanaged symptoms or clinical problems, they will be referred to their health care provider per protocol. Should the participant become ill, causing them to miss three consecutive exercise interventions, the participant will be instructed to call their nurse, who will reevaluate and adjust the exercise prescription per protocol. Should the primary nurse intervener become ill or unable to meet with participant, a pre-assigned secondary nurse intervener will step in. There could be diffusion of treatment effects between IIG, WCG, and ACG as well as confounding effects if a disproportionate number of physically active participants are assigned to the IIG, WCG, or ACG. We will assess functional capacity levels and use block randomization to minimize these effects.

Table 4. Research Timeline	Year 1				Year 2				Year 3				Year 4				Year 5			
Activities	Q1	Q2	Q3	Q4																

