Our **long-term goal** is to develop interventions to increase perceived self-efficacy (PSE), perception of ability, for CRF self-management as a means of improving functional status and quality of life for persons with NSCLC.²⁵ Our **objective** in this application is to determine the efficacy, optimal timing of initiation, and sustainability of our 6-wk home-based exercise intervention. The **significance** of this study is that it targets two of the most troublesome unmet needs, fatigue and lack of exercise, in an understudied, vulnerable population with the potential to **transform** the current standard of care by providing a rehabilitative exercise intervention after surgery. The proposed research advances the field by providing both an intervention for CRF self-management and evidence for its optimal initiation and sustainability, which currently does not exist for the post-thoracotomy NSCLC population. Our exercise intervention is guided by a theoretical approach (tested by the PI) incorporating self-efficacy theory to strengthen a person's ability to manage their CRF and walking ability.^{17,26} The exercise intervention is **innovative** in its timing and approach in providing self-paced exercise to a vulnerable post-surgical NSCLC population upon discharge from the hospital. The Nintendo's Wii Fit Plus is used to provide light-intensity, virtual reality walking and balance exercise that departs from the status quo and transcends barriers to exercise, as demonstrated by our R21 RCT retention and adherence outcomes.

This study employs a three-arm RCT for persons undergoing NSCLC surgery with participants being randomly assigned to an immediate (post-hospital discharge) exercise intervention group, a wait-list control group (6 wks usual care [wks 1-6] and 6 wks exercise [wks 7-12]), or a 6 wk attention control group (wks 1-6).

Protocol Version 4.0 (7/19/2023). UNMC IRB 560-18 EP. Contact PI: [name] [name], RN.

Primary Outcome: Cancer-Related Fatigue (Severity and Fatigability).

Secondary Outcomes: Severity of Other Symptoms; PSE for CRF Self-Management, Walking, and Balance; Functional Performance; and Quality of Life (QOL).

Aim 1: Determine efficacy of three groups by comparing: 1) immediate exercise intervention group; 2) a wait-list control group; 3) an attention control group by age. Hypothesis 1: The exercise intervention group will outperform wait-list and attention control on all primary and secondary outcomes at wk 6 for all ages.

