5B) Setting & Sample. The target sample will be recruited in **5 sites**. We will continue the working relationships we built while conducting our R21 RCT with Spectrum Health, McLaren, and Sparrow Health. We will add Munson Healthcare and Nebraska Medicine Campus. Results from our R21 RCT show very large effect sizes between the exercise and usual care groups that are not expected to hold in this proposed study as we have additional sites with more diverse populations and two new study arms (ACG and WCG). Our sample size assessment for primary Aim 1 uses the expected CRF severity scores by age group shown in **Table 1 (below)** with CRF estimates from our R21 RCT for comparison. An exemplar multiple regression model was run with age distribution approximating the NSCLC population with 33% < 65 yrs and 67% ≥ 65 yrs, model error standard deviation (SD) = 2.0. Comparable R21 results suggest a SD between 0.7 and 2.6 in these two age groups. With overall significance level at 5%, we computed the total sample size N to ensure at least 80% power in 4 pre-specified comparisons between IIG and ACG for ages <65 and ≥ 65. With N = 180 (60/group, 20 <65 yrs and 40 ≥ 65 yrs) power to detect the expected CRF is shown in **Table 2 (below)** with the minimum sample size for each comparison. Based on our R21 RCT and previous cancer work,¹¹⁵ we will over-recruit to account for a conservative attrition rate of 20% (N = 225 = 180/0.8), and under plausible assumptions,^{116,117} conservatively provide for 90% compliance increasing for a total of N = 279 ≈ 225/(0.9)(0.9)¹¹⁷ patients.

Table 1: Expected mean CRF Severity scores at 6 weeks post-surgery by age

Group	Age	CRF-Expected	CRF-from R21
IIG	<65	2.5	0.81
IIG	65+	2.0	0.68
WCG	<65	4.5	4.12
WCG	65+	4.2	3.99
ACG	<65	4.3	4.12
ACG	65+	4.0	3.99

Table 2: Power to detect expected differences in mean CRF Severity scores between groups by age

Comparison	Age	Power (N=180)	N for 80% power
IIG vs ACG	<65	0.81	180
IIG vs WCG	<65	0.88	144
IIG vs ACG	65+	0.94	81
IIG vs WCG	65+	>0.99	63

5C) Study Protocol

The following protocol was used successfully in our R21 RCT with the addition of the WCG and ACG in the proposed study. Participants scheduled for NSCLC surgery will be identified by the surgeon's office prior to surgery, recruited, and enrolled by the nurse recruiter.

5C1) Study Interventions.

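### Aim 1 has two primary outcomes, two controls and two age strata but no rule for combining them, so the 5% overall level is not secured and the stated power covers single CRF-severity contrasts only

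*Combined protocol and SAP*

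**What the plan says.** - **Outcomes and hypothesis (Section 1.0).** CRF severity and fatigability are listed together as the primary outcome. Hypothesis 1 then joins outcomes, controls and ages: "The exercise intervention group will outperform wait-list and attention control on all primary and secondary outcomes at wk 6 for all ages".
- **Sample size (Section 5B).** "Our sample size assessment for primary Aim 1 uses the expected CRF severity scores by age group". Table 1 holds CRF-severity means, Table 2 holds CRF-severity power, and the model error SD of 2.0 belongs to that outcome. The text adds: "With overall significance level at 5%, we computed the total sample size N to ensure at least 80% power in 4 pre-specified comparisons". It describes those comparisons as immediate intervention group (IIG) against attention control (ACG) in the two age groups, while Table 2 also lists the wait-list control (WCG).
- **Fatigability (Section 7.0).** It is defined as average walk-test fatigue divided by walking velocity. No expected mean, SD, effect or power for this ratio is given anywhere.
- **Analysis (Section 10.0).** "Primary analysis (Aim 1) is the comparison among study groups of the primary outcome CRF severity and fatigability", by regression on baseline CRF, study group and age, with interactions if appropriate, testing study group. On level: "All tests of hypotheses will be two-tailed at" 0.05. The section refers back to 5B for sample size and contains no rule across outcomes, controls or age groups.

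**The concern.** Two things depend on the missing rule, and they pull in opposite directions. If success on either primary outcome supports Aim 1, two outcomes at 0.05 each give more than a 5% chance of a false claim. If success must be shown on everything that Hypothesis 1 names, the chance of success is lower than any single entry in Table 2, and for fatigability it is unknown. The plan does not choose, so the choice could be made after the results are seen. The point remains however the four CRF-severity comparisons are handled among themselves, because fatigability lies outside them.

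**Working it through.** **Inputs.** From 5B: 20 participants under 65 and 40 aged 65+ per arm, SD 2.0. From Table 1, the differences IIG-ACG are 4.3 - 2.5 = 1.8 (<65) and 4.0 - 2.0 = 2.0 (65+); IIG-WCG are 4.5 - 2.5 = 2.0 (<65) and 4.2 - 2.0 = 2.2 (65+). Two-sided 0.05.

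**Step 1: reproduce Table 2.** Standard error = 2.0 × √(2/n), which is 0.632 for n = 20 and 0.447 for n = 40. Power ≈ Φ(difference/SE - 1.96).

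| Contrast | Difference/SE | Computed | Table 2 |
|---|---|---|---|
| IIG vs ACG, <65 | 2.85 | 0.81 | 0.81 |
| IIG vs WCG, <65 | 3.16 | 0.885 | 0.88 |
| IIG vs ACG, 65+ | 4.47 | 0.994 | 0.94 |
| IIG vs WCG, 65+ | 4.92 | 0.998 | >0.99 |

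Three entries reproduce at an unadjusted 0.05 per comparison. The 0.94 does not follow from Table 1, but the discrepancy does not affect N, which the first row sets. With a Bonferroni level of 0.05/4 = 0.0125, the first row would be 0.64. So Table 2 carries no adjustment for four comparisons.

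**Step 2: joint power for CRF severity.** The two contrasts within an age stratum share the IIG arm, so their correlation is 0.5; the strata are independent. Simulating arm means with these inputs:

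- both contrasts, <65: 0.75
- both contrasts, 65+: 0.99
- all four: 0.74 with t critical values on 174 degrees of freedom, 0.75 with normal ones.

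The loss is almost entirely in the younger stratum of 20 per arm.

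**Step 3: pool the ages, 60 per arm.** The average IIG-ACG difference is (20 × 1.8 + 40 × 2.0)/60 = 1.93. The standard error is 2.0 × √(2/60) = 0.365, so the ratio is 5.3 and power exceeds 0.99. For IIG-WCG the average difference is (20 × 2.0 + 40 × 2.2)/60 = 2.13, and power again exceeds 0.99.

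**Step 4: family-wise error with no true effect, ages pooled.** The correlation between the two primary outcomes is not in the documents; 0.3-0.7 is assumed.

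- One study-group test per primary outcome at 0.05: independent outcomes would give 1 - 0.95² = 9.75%. At correlation 0.7 to 0.3, simulation gives 8.5-9.6%.
- Two outcomes by two controls, each pair tested at 0.05 with no preceding group test: four independent tests would give 1 - 0.95⁴ = 18.5%. With the shared arm and correlated outcomes, simulation gives 14-16%.
- The same four tests, counting only false claims that exercise is better: the independent bound is 1 - 0.975⁴ = 9.6%; simulation gives 7-8%.

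All three exceed 5%.

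**The case against.** The strongest reply is that Hypothesis 1 is an expected direction and not a success criterion. The expected-benefits text and Section 6.0 repeat it as an expectation, and Section 10.0 plans a test of study group with age in the model, for which CRF severity has power above 0.99. That stands. A reader might infer that the trial must win on every outcome and would often fail with a true benefit of the planned size. The documents do not support that, because no passage makes significance everywhere the criterion. What the reply does not supply is the criterion itself. Section 5B also computes power within age strata, so the age-specific reading cannot be dismissed.

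A reader might also put joint power well under 80% by adding fatigability. Taking the pilot walk-test fatigue difference of 2.7 with the control-arm SD of 1.5, diluted as Table 1 dilutes CRF severity (1.8/3.31 to 2.2/3.31, or 54-66%), gives 0.64-0.68 for both primary outcomes in all four contrasts. That figure rests on fatigue alone standing in for the fatigue/velocity ratio, an assumed dilution and an assumed correlation. With the SD pooled over both pilot arms (1.19), it becomes 0.72-0.74. If the full pilot effect held (d = 1.8), adding fatigability would cost nothing, although 5B itself does not expect pilot effects to hold. No firm figure below 0.74 can be drawn from the documents.

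On error, 14-16% applies only to ungated pairwise testing in both directions. Section 10.0 describes a study-group test, so 8.5-9.6% is closer to the plan as written.

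**Conclusion.** The point holds as a missing decision rule with two measurable consequences. First, the overall 5% in 5B is not secured across the two primary outcomes: about 8.5-9.6% with one group test per outcome, and 14-16% with unprotected pairwise tests (7-8% for false claims of benefit), at an assumed outcome correlation of 0.3-0.7 and with ages pooled. Second, if every contrast is required, the plan's own inputs give 0.74 for the four CRF-severity contrasts. That is a ceiling for the strictest reading of Hypothesis 1, and it comes from the <65 stratum. Fatigability has no stated power under any reading. It does not follow that the trial is underpowered for its main comparison: for CRF severity with ages pooled, power exceeds 0.99 against each control.

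**What to change.** In Section 10.0, restate Hypothesis 1 as a decision rule for Aim 1:

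1. Test CRF severity at week 6 first, because it is the outcome on which the trial was sized.
2. Test fatigability second, at 0.05, only if CRF severity succeeds.
3. State whether success requires both controls or one, and whether pooled or age-specific contrasts decide it. The sequence alone does not hold 5% if any one of several contrasts within an outcome may count.
4. Report secondary outcomes with confidence intervals as supportive.

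In Section 5B, state that Table 2 covers CRF severity only, as power per single comparison at unadjusted 0.05. Give 0.74 as the joint figure for all four contrasts, and state that no power is given for fatigability. Do not print a joint figure including fatigability unless an expected ratio and SD can be justified.

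The cost is protocol and SAP wording, with no added participants or data. A fatigability claim would then depend on CRF severity succeeding, and the stated power would look slightly less favourable. Splitting alpha or requiring both outcomes would also settle the matter; the sequence is suggested because it keeps the full 0.05 for the sized outcome.
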